5.2. Overview of Study Visits (Table 2)

The following table provides a general overview of the study visits:

	Baseline	CBT (6 sessions daily sessions)	Post- Treatment	1 month follow- up	4 month follow- up	8 month follow- up
Consent	X					
Interviews	X			X	X	X
Questionnaire s	X		X	X	X	X
Talk therapy		X				
Duration	1-2 hours	1-1.5 hours Ea session	2-2.5 hours	2-2.5 hours	2-2.5 hours	2-2.5 hours
Protocol Days	1	2-7	8	40	130	250
Payment	\$25	\$5 per completed session	\$25	\$50	\$100	\$100

6.0 STUDY PROCEDURES

6.1. Recruitment Strategy. Strategy: We will recruit individuals entering residential treatment for an alcohol use disorder at the Fairview Hospital Chemical Dependency program (Lodging Plus) for adults in Minneapolis. Participants will be recruited from the Consortium of Addiction Research (CAR) combined screening process, approved as IRB protocol #STUDY00005170. Complete details of the screening process can be found in the protocol for that study. Those who are eligible based on the CAR screening protocol will be invited to participate via the “1404S49427 Invite” and given a copy of the consent form. At the Baseline appointment they will have time to read the consent form and have their questions answered. In addition, they will watch a brief video of the study PI describing key elements of the study. If the staff person conducting the screening appointment is convinced the individual understands the consent form based on their answers to questions highlighting the key elements of participation, the individual will be offered the opportunity to sign the consent form. After signing the Consent Form, the baseline appointment will be completed and the appointments for the CBT therapy will be arranged.

Lodging Plus evaluates approximately 1000 chemically dependent patients per year, approximately 70% of whom are seeking treatment for alcohol dependence. Based on our experience in the parent R01 (see above), we should be able to recruit about two patients per week and a total of about 90-100 patients per year. Based on this, the target sample of 350 will be recruited in slightly less than 4 years. Our attrition rate over the entire life of the study was about 20% but was approximately 15% in the final year. (Note improvements in recruitment and retention over the course of the parent R01 reflects refined and improved methods based on our accumulating experience.) Based on the attrition estimate of 15%, we would have approximately 300 cases with four-month follow-up data, which will well power the study (see power estimates below).

6.2. Participant Selection

6.2.1 General description of participants anticipated. Male and female ages 18-65 will be recruited from among those individuals seeking treatment for an alcohol use disorder at the Fairview Hospital Chemical Dependency program (Lodging Plus) for adults in Minneapolis. Based on our earlier studies conducted in this same population and program, we anticipate that the mean age of participants will be approximately 39 years old. The sample will be 40% female with 83% self-described as Caucasian, 10% African American, 5% American Indian, 1% Hispanic, and 1% Asian. We are seeking to recruit 350 individuals over a 48 month period.

6.2.2. Lodging Plus alcohol use disorder (AUD) treatment as usual (TAU). As noted, all patients will be selected from incoming patients at the Lodging Plus TAU. Individuals from whom we will attempt to recruit will undergo the Lodging Plus TAU whether or not they participate in the research. The AUD TAU program is based on the “Minnesota Model” in which the primary goal is lifetime abstinence from alcohol with therapies based on principles of the 12-step philosophy, including frequent meetings with other recovering people, repair of family relationships, healthy changes in daily behaviors and attention to spiritual growth. Treatment programming primarily takes place in 1 hour group sessions with programming from 8:30 a.m. to 4:30 p.m., with two, one-hour breaks during the day, Monday through Friday. (All study activities involving patients take place during patient free-time when there is no conflicting programming).

6.3. Screening

6.3.1. Participant Screening:

We will recruit individuals entering residential treatment for an alcohol use disorder at the Fairview Hospital Chemical Dependency program (Lodging Plus) for adults in Minneapolis. Participants will be recruited from the Consortium of Addiction Research (CAR) combined screening process, approved as IRB protocol #STUDY00005170. Complete details of the screening process can be found in the protocol for that study.

6.3.2 Consent (10 minutes): Those who are eligible based on the CAR screening protocol are next given the consent form and baseline appointment invitation via a sealed note slipped under the door of their semi-private bedroom on Lodging Plus or handed to them if they answer their door when the staff member knocks. The note will be marked “Confidential” and will be stapled shut with only their first name, last initial, and room number visible. They will be directed to read the Consent Form and at the Baseline appointment the staff member will answer their questions and clarify through a set of pre-determined questions whether the individual understood the key tasks, risks and benefits of participating described in the consent form. In addition, they will watch a brief video of the study PI

describing key elements of the study. If the individual understands these details and chooses to sign the consent form, they next undergo the baseline assessment described in section 6.4.2. These activities take place during the patients free time in the Lodging Plus program (i.e., no conflicting programming) in the Ambulatory Research Center on the 2nd floor of the Fairview West building (a location on a different floor in the same building as the Lodging Plus program that is private relative other LP patients or staff members).

6.3.3. Inclusion criteria include:

- a) DSM IV diagnosis of PD, GAD, and/or SAD within the past 30 days;
- b) inpatient treatment at Lodging Plus primarily for alcohol (vs. other drug) dependence
- c) alcohol use in the 30 days preceding the study
- d) ability to provide informed consent
- e) minimum of a sixth grade reading level (deemed necessary to complete study materials);
- f) Willingness to provide contact information to confirm study follow-up appointments
- g) Lives within proximity to the Twin Cities (e.g., within about an hour's drive) for the purpose attending follow-up visits
- h) between the ages of 18 and 65

6.3.4. Exclusion criteria include:

- a) lifetime history of psychosis or mania by history
- b) cognitive or physical impairment that precludes study participation
- c) currently and seriously suicidal (i.e., plan and intent)
- d) primary PTSD as determined by the qualifying assessment or borderline personality disorder as determined by the screening form
- e) In Lodging Plus because they were court ordered to receive chemical dependency treatment.

Note that all inclusion and exclusion criteria is assessed as part of the Consortium of Addiction Research combined screening process approved as IRB protocol #STUDY000005170.

6.4. Assessments: (about 2 hours for each assessment including Baseline, Post-Treatment, 1-mo, 4-mo and 8-mo follow-up assessments; see Table above). A general description of the task of each assessment is given here with a fuller

6.4.1 Interviews/Diagnoses

a). Structured Clinical Interview for DSM IV (SCID). (45 minutes) Selected modules from the SCID to determine diagnostic status with reference to anxiety disorders, depression and alcohol/drug use disorders. The SCID is essentially a checklist of psychiatric diagnostic criteria (i.e., symptoms and problems) that are rated by the interviewer as "present," "absent" or "sub-clinical" or "in-determinant." This is administered at the follow-up appointments of the study.

b) Timeline Follow-Back (TLFB). (15 minutes) The TLFB interview will be used in all primary assessment to identify daily drinking patterns of patients in the four months before treatment and in the intervals between study assessments. Using a calendar, the respondent provides retrospective estimates of daily drinking over a specified amount of time.

6.4.2 Questionnaire Packets (1 to 1.5 hours) (Each questionnaire takes about 5 minutes to complete and typically includes 20 multiple choice questions or less) (References and rationale for questionnaires are provided below).

a) Anxiety.

- State-Trait Anxiety Inventory (STAI)
- Penn State Worry Questionnaire (PSWQ)
- Beck Depression Inventory (BDI)
- Panic Disorder Severity Scale (PDSS)
- Social Phobia Scale (SPS)
- Inventory of Depression and Anxiety Symptoms (IDAS)
- Perceived Stress Scale (PSS)

b) Alcohol.

- Alcohol Expectancy Questionnaire (AEQ)
- Inventory of Drinking Situation (IDS)
- Situational Confidence Questionnaire (SCQ)
- Obsessive-Compulsive Drinking Scale (OCDS)
- Addiction Severity Index (ASI)
- Reasons for Drinking Questionnaire (RFDQ).
 - Drinking to Cope Questionnaire (DCQ)
 - Negative Emotions and Use Questionnaire (NEUQ)

c) Other

- Demographics
- Treatment Services Summary (TSS)
- Suicidality Questionnaire (SQ)
- Personality Inventory for DSM-5 Brief Form (PID-5)

6.5. The CBT Therapy (six daily one-hour sessions)

6.5.1. Background of the CBT and modifications pertinent the proposed work. The CBT treatment used in the parent R01 (see Kushner et al., 2013) included three 1-hour anxiety reduction sessions (AR content set) and three 1-hour alcohol-anxiety de-coupling sessions (DC content set). Parallel clinical domains are addressed in both the AR and DC content sets focused on: 1) cognitive restructuring; 2) coping skills training; and, 3) practice with exposure/habitation. The material for the AR content set was synthesized from a survey of published work related to the bio-psycho-social model of anxiety (e.g., Barlow, 2001; Barlow et al., 1989), cognitive restructuring of anxiety related cognitions (e.g., Beck, 1976; Beck et al., 2005; Ellis & Harper, 1975), breathing retraining for coping with anxiety (e.g., Han et al., 1996), and exposure for habituating conditioned anxiety responses (e.g., Foa & Kozak, 1986). The material for the DC content set was synthesized from published work related to the vicious cycle model of alcohol and anxiety (e.g., Kushner et al., 2000a), cognitive restructuring of alcohol-related beliefs and expectancies (e.g., Beck et al. 1993, Kushner et al., 2000b), alternatives to drinking for coping with anxiety (e.g., Larimer et al., 1999), and exposure for habituating conditioned associations between anxiety and alcohol cues (e.g., Cooney et al., 1997; Litt et al., 1990; Sinha, 2009). The therapy doses chosen in the parent R01 (3 sessions for anxiety reduction and 3 for alcohol-anxiety de-coupling for 6 total sessions) represented a balancing of

competing interests in delivering therapeutic levels of the interventions for both theoretically central mechanisms (anxiety reduction and anxiety-alcohol de-coupling) while: 1) not interfering with the full day of standard AUD programming; 2) beginning at least one week after detoxification to accommodate recruitment time and to ensure therapy is delivered post-acute detoxification; and, 3) concluding treatment prior to discharge from the 28-day residential AUD program to avoid conflicts with re-location, return to place of employment, transportation etc. These parameters will apply to the renewal project conducted in the same institutional setting as the parent R01. The CBT-O group in the renewal work will be the same CBT protocol used in the parent R01; i.e., the three-session AR content set plus the three-session DC content set for a total of six sessions. The two dismantled CBT therapy conditions will include one of the three-session content sets (AR or DC) plus one additional session devoted to each of the three clinical domains (cognitive restructuring, coping skills, and exposure/habituation) within that set for a total of six sessions for all therapy groups.

6.5.2. Elements common to all three CBT therapy group conditions:

a) Psycho-Education in which the participant is introduced to the basics of the CBT model of therapy. This portion of the treatment is largely didactic and includes powerpoint slides that are narrated by the therapist.

b) Cognitive Coping Skills in which the participant is taught how to distinguish between thoughts, feelings and situations that are associated with negative affect (i.e., stress, anxiety and depression) and how each of these components interact with the others. Participants are then taught and practice a standard CBT skill referred to as "cognitive-restructuring" in which thoughts and beliefs that aggravate negative affect through their inaccuracy, incompleteness, or exaggeration are systematically examined and modified to better align with probabilistic reality and logical inference. This process has been shown in 100s of separate studies to improve anxiety and depression symptoms in psychiatric patients.

c) Behavioral Coping Skills in which the participant is taught behavioral strategies to reduce negative affect and tension. These include slow-paced diaphragmatic breathing and "behavioral activation." Behavioral activation is an intervention in which goals identified as important by the participant in several domains of life (e.g., social, health, occupational, educational) are identified and a specific realistic plan of activities aimed at moving toward those goals is developed. Past studies in psychiatric patients have shown that engaging in behavioral activation relieves negative affect and improves life satisfaction.

d) Coping Skills Practice with Guided Imagery exposure in which participants will have the opportunity to apply cognitive and behavioral coping skills while imagining being in a common situation in which they have experienced moderate negative affect associated with their anxiety disorder. The actual content of the guided imagery exercise is provided by the participant with explicit instructions and therapist guidance aimed at avoiding content related to extreme distress such as that associated with trauma. Using guided imagery "exposure" in this way is a standard component of CBT used when real life (in-vivo) exposures are too intense or are not feasible; as will generally be the case while residing at Fairview hospital during the course of the CBT. It is generally found that imagery based exposures of this sort are less intense than actually being in the situation imagined. Also, it is a central tenet of CBT that therapeutic skills that are practiced while being in stressful situations (or imagining them in this case) are more clinically effective; i.e., are more likely to be deployed at all or to be deployed effectively when real-life stressors occur. The PI is a licensed

psychologist and practicing CBT therapist who has routinely used this and other CBT techniques described for over 20 years.

e) Post therapy session knowledge quizzes will be given after each session to document that the participant understood the major points covered in that session. These quizzes are designed to be easy to answer correctly if the patient was actively participating in the session. The therapist will provide immediate feedback on the quiz and will emphasize why another answer is considered correct if any questions are answered incorrectly.

f) Between session practice and monitoring will be assigned following each of the six CBT therapy sessions that will focus on practicing the skill taught in the session and keeping a simple record of their anxiety level and urge to use alcohol between the sessions as well as whether they were able to effectively use the therapy skill to reduce the negative affect/urge.

6.5.2. Elements distinguishing the three randomized CBT therapy group conditions:

a) CBT-Anxiety Reduction Condition: Those assigned to this group will undergo all of the CBT elements outlined above but with all six sessions focused on negative affect without specific reference to alcohol alcohol use.

b) CBT Anxiety-Alcohol Interaction Condition: Those assigned to this group will undergo all of the CBT elements outlined above but with all six sessions focused on the interaction of negative affect with alcohol use/urges.

c) CBT Combination Condition: Those assigned to this group will undergo all of the CBT elements outlined above but with three of the six sessions focused exclusively on reducing negative affect without reference to alcohol use and the other three sessions focused exclusively on the interaction of negative affect with alcohol use/urges.

6.5.3. Therapist training. The study PI is primarily responsible for training and supervision of study therapists. The training sequence established in the parent R01 will also be used in the renewal work including: 1) reading the therapist and patient treatment manuals; 2) observing training tapes that have been prepared for that purpose; 3) observing the trainer administer the treatment; and 4) being observed and critiqued by the trainer while delivering the treatment. Our experience suggests that delivery of the therapy via the structured PowerPoint slideshow (above) ensures a uniform delivery of the basic content of the therapy, even with newly trained therapists. Supervision with the PI takes place on a weekly basis throughout the treatment phase of the project (separately for each therapist) in which the progress of each case is discussed and any treatment issues are resolved.

6.5.4. Therapy compliance and fidelity. The renewal project is fortunate to have added a new Co-I, [name], who has served in the role of therapy compliance and fidelity assessment in substance abuse treatment protocols using psycho-social interventions. All therapy sessions will be recorded and a randomly selected 15% will be reviewed by [name] according to a checklist and scales modified after the *Yale Adherence and Competency Scale (YACS) (2nd ed)* (Di Rezze et al., 2012; Nuro et al., 2005). The YACS “is a general system for rating therapist adherence and competence in delivering behavioral treatments for substance use disorders” (p. 1). Fidelity checklists and scales will include prescribed and proscribed content, as well as therapy processes (Waltz et al., 1993). All deviations from the therapy protocol, especially contamination across treatment conditions, will be addressed at weekly supervision sessions with the research therapists. The PI will decide whether any protocol violation identified warrants remedial training for the therapist and the implications for data integrity. All such violations will be logged and incorporated into final data reports (Perepletchikova

et al., 2009). As of September, 2016, [name], M.A., a former therapist for this study, took over the role of therapy compliance and fidelity checks from [name].

6.6. Treatment Duration

The study treatment lasts for six consecutive business days, which, given weekends and occasional interruptions due to things such as family meetings, illness, and outside appointments leads us to reserve 10 days to complete the six sessions. These sessions all take place while the participant is a residential patient in the Fairview Lodging Plus AUD TAU, which is typically a 28-day treatment program.

6.7. Study Duration

6.7.1. Grant funding period. The grant is being funded for a period of 60 months (5 years). (See Table 2 above)

6.2.2. Projected timeline of grant-related activities. See Table 1 above for the projected timeline of all primary study phases.

6.8. Measures. All assessments (except for the qualifying assessment) are identical. However, the timeframe around which interview questions are posed refers to "since your last assessment.

6.8.1. Screen for current intoxication. If we suspect that a patient is intoxicated, blood alcohol concentration will be measured using the AlcoMate Core Breathalyzer measures BAC% between 0.00% and 0.40% in 0.01% steps. Sensor accuracy of the AlcoMate is +/- 0.005% BAC. This measure will be taken prior to any study related interactions with patients to insure they are not intoxicated at the time. If a patient's BAC is above .04% scheduled tasks for that day will be rescheduled. If the patient is driving their self, alternative arrangements will be made for their transportation home and arrangements will be made with parking services to allow their car to remain on the facilities for up to 24 hours at no cost to the patient.

6.8.2. The Structured Clinical Interview for DSM IV (SCID): The SCID (First et al., 1989) will be used to establish all relevant study diagnoses during the STUDY000005170 screening process and at follow-up appointments. Diagnostic modules include panic disorder (with or without agoraphobia) (PD), social anxiety disorder (SAD), generalized anxiety disorder (GAD), major depressive disorder (MDD), post-traumatic stress disorder (PTSD), alcohol dependence (AD) and drug *dependence* (DD). The SCID will also be slightly modified to establish a "principal" anxiety disorder (PD, SAD, or GAD) for those participants with more than one of the inclusionary anxiety disorders (Andrews et al., 2002). A qualified SCID trainer (includes the PI and Co-I, [name]) will be responsible for training the *blinded assessor* in the valid use of the SCID using standard training materials (First et al., 1989). All diagnostic decisions will be made using a clinical consensus model with the PI adjudicating any cases in which the team could not reach consensus. All interviews will be videotaped and 15% will be double-scored to index reliability (Co-I, [name] will oversee this along with therapy fidelity).

6.8.3. The Time Line Follow-Back (TLFB). The TLFB interview (Sobell & Sobell, 1995) will be used to identify daily drinking patterns of patients in the four months before treatment and in the intervals between study assessments. The TLFB has been shown to have adequate psychometric *qualities* in both clinical and non-clinical populations (Sobell & Sobell, 1995). Using a calendar, the respondent provides retrospective estimates of daily drinking over a specified amount of time. All primary and

secondary alcohol outcomes, with the exception of alcohol dependence from the SCID, will be derived from the TLFB assessment including: 1) any use vs. abstinence; 2) *percent or number (depending on the distribution) days drinking per month*; 3) *number of drinks per drinking day; and, 4) NIAAA-defined “hazardous drinking” (for men: > 4 drinks in a day or 14 drinks in a week; for women: > 3 drinks in a day or 7 drinks in a week) status.*

6.8.5. Anxiety questionnaires. Because we recruit patients with a variety of anxiety disorder subtypes characterized by a distinct constellation of anxiety symptoms (i.e., generalized anxiety disorder, social anxiety disorder or panic disorder with or without agoraphobia), it is challenging to find a single index that reasonably characterizes anxiety levels for the entire sample. Based on work in the parent R01, we have identified several solutions to this problem. First, in Kushner et al. (2013-a) we used the State and Trait Anxiety Inventory (STAI) (Spielberger et al., 1999) as a general measure capable of representing anxiety-related dysfunction across the range of specific anxiety disorders included (c.f., Oei, et al., 1990). Second, in Kushner et al. (2013-b) we showed that multiple domains of internalizing psychopathology symptoms – Penn State Worry Questionnaire (Meyer et al., 1990); Beck Depression Inventory (Beck et al., 1961); Panic Disorder Severity Scale (Houck et al., 2002); Social Phobia Scale (SPS) (Brown et al., 1997); Mobility Inventory (Chambless et al., 1985); State and Trait Anxiety version of the State-Trait Anxiety Inventory (STAI) (Spielberger et al., 1999) – can be well represented by two latent factors labeled “fear” and “distress.” By establishing that these latent structures were invariant across time and treatment, we demonstrated they could be used to quantify treatment effects. A third approach uses SCID-based anxiety diagnoses: 1) determining at FU the participant no longer meets diagnostic criteria for the qualifying (principal) anxiety disorder diagnosis; or, b) determining at FU the participant no longer meets diagnostic criteria for any of the three inclusionary anxiety disorder diagnosis assessed. Each of these approaches to quantifying change in anxiety by group will be utilized; however, latent fear and distress measures will constitute the primary anxiety process measures (see Data Analysis section below).

6.8.6. Alcohol-anxiety de-coupling questionnaires. The following measures will be used to quantify change in alcohol-anxiety de-coupling: 1) Expectancies - the Alcohol Outcome Expectancy Questionnaire (OEQ) (tension-reduction scale) (Leigh & Stacy, 1993); 2) Coping - the Situational Confidence Questionnaire (SCQ) (unpleasant emotions and social tensions subscales) (Annis, 1988); 3) Conditioned Associations - the Obsessive-Compulsive Drinking Scale (OCDS) (Flannery et al., 1999, 2001).

6.8.7. Determinants of relapse measures. The Reasons for Drinking Questionnaire (RFDQ) (Zywiak et al., 1996) will be employed at BL and all FUs to establish scores on participants’ reasons for drinking. At BL, the 16-item questionnaire will be referenced to their “typical drinking” in the past 4 months (reasons for drinking). At the FU’s, the questionnaire will be referenced to the first use of any alcohol since the previous assessment and also to any other uses of alcohol after at least 14 days of abstinence, as was done in Project MATCH (e.g., Zywiak et al., 2006). Based on factor analytic work produced by Zywiak et al. (2003), the RFDQ will be scored using three subscales including: 1) Negative Affect; 2) Social Pressure; 3) Craving/Cued. Each relapse assessed at follow-up will use the Zywiak et al. (2003) scoring algorithm to obtain both a continuous score on each subscale and a categorical assignment on one scale as the primary determinant of the relapse.

6.8.9. Close-Call Interview. An investigator-developed close-call interview will be administered at all follow-ups to obtain information on “close-call” relapse situations (i.e., situations in which the

participant believes they were at risk of using alcohol ("relapse") but managed to refrain) as well as the therapy "tools" the participant used (if any) to avoid the relapse. This information will be useful to evaluate the effectiveness of the tools we are currently teaching and to help identify areas in which we may need improvement.

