7.5. Primary Aim: To compare the CBT-DC and CBT-AR groups on alcohol outcomes

We predict that the CBT-DC group will have superior alcohol outcomes compared to the CBT-AR group. The primary intention to treat (ITT) population will include all patients randomized. The per-protocol (PP) population will include patients who completed at least four of six (66%) of the therapy sessions with CBT-O patients not missing any more than one of the three AR or DC content sessions. Hypotheses based on the vicious cycle model and parent R01 findings suggest that without alcohol-anxiety de-coupling therapy, drinking relapse is more likely to occur and more severe when it does occur. Therefore, we consider as primary outcomes both categorical relapse status (yes vs. no) and continuously measurement of relapse severity (percent/number days drinking and drinks per drinking day). Secondary alcohol outcomes tested include categorical status on: a) alcohol dependence (yes vs. no) and hazardous drinking (yes vs. no). Follow-up assessments occur 1-, 4- and 8-months following the conclusion of the study therapy and are keyed to the time since the last assessment. To align study findings with the parent R01, the primary assessment point will be the 4-month FU. However, hypotheses will also be tested across all time points to establish temporal patterns of group effects. We test the hypotheses using mixed effects models if data residuals are

normally distributed and generalized estimating equations (GEE) if the data are non-normally distributed (Gueorguieva, & Krystal, 2004; Liang & Zeger, 1986). Both are flexible regression methods for incomplete repeated measures data and allow continuous and categorical covariates, fixed and time-dependent covariates, and a specification of unstructured as well as structured covariance matrix. Categorical outcomes will be evaluated using chi-square tests of proportions and logistic regression, with statistical significance criterion also set at $p < 0.05$. Zero-inflated negative binomial analyses will be used to contrast the study groups on count variables if warranted by a high percentage of zero alcohol use days over the follow-up (e.g., Agresti, 2002).

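### The PI, who can be expected to know the arm, settles disputed follow-up SCID diagnoses, and no masking at adjudication is specified; this touches alcohol dependence but not the TLFB outcomes.

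*Combined protocol and SAP*

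**What the plan says.** **Diagnosis.** Section 6.8.2 uses the SCID both at screening and at follow-up appointments, and its modules include alcohol dependence and the three inclusionary anxiety disorders. The assessor is described as blinded. Every diagnostic decision then goes to clinical consensus, "with the PI adjudicating any cases in which the team could not reach consensus". The rule does not separate screening from follow-up.

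**The PI's other role.** Section 6.5.3 states: "The study PI is primarily responsible for training and supervision of study therapists". Supervision is weekly and separate for each therapist, "in which the progress of each case is discussed and any treatment issues are resolved". Under Section 6.5.4, deviations from the therapy protocol, "especially contamination across treatment conditions, will be addressed at weekly supervision sessions with the research therapists". The same section adds: "The PI will decide whether any protocol violation identified warrants remedial training for the therapist and the implications for data integrity".

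**Outcomes that use these diagnoses.** Section 6.8.3 takes every alcohol outcome from the TLFB except alcohol dependence, which comes from the SCID. Section 7.5 lists alcohol dependence as secondary; Section 5.1 names it among the primary relapse measures. Section 6.8.5 gives SCID-based remission as the third of three ways to measure anxiety change and makes the latent fear and distress factors primary.

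**The concern.** The plan protects the SCID by blinding the person who gives it, then gives the last word on cases the team cannot agree to someone who works with the therapists on those same cases. Those are the cases where the criteria settle least and judgement counts most. The protocol also predicts an ordering of the arms on alcohol outcomes: CBT-DC best, then CBT-O, then CBT-AR. An adjudicator who knows the arm and holds that prediction can shift borderline dependence diagnoses without intending to. What is at stake is the credibility of one alcohol outcome, whose rank the document leaves unsettled, and of a supportive anxiety measure.

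**Working it through.** The plan states no figure on this point, so the check is a comparison of the text followed by an illustration of size.

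**1. Does the PI know the arm?** The document never says so directly. It does say that the PI discusses each case with its therapist and that contamination between conditions is taken up in those sessions. Section 6.5.2 makes the arms differ openly: CBT-AR leaves alcohol out of all six sessions, CBT-DC deals with its interaction with negative affect in all six, and CBT-O does so in three. It is hard to supervise a case, or to judge contamination in it, without knowing which content was assigned.

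**2. Is the PI masked when adjudicating?** Four places might suggest it.
- Section 6.8.2 applies the word blinded to the assessor only.
- Table 1 schedules breaking the blind in months 49 to 54 but does not say whose blind.
- Sections 6.11.5 and 8.3.2 stop the PI and DSMB from assessing efficacy and feasibility data by treatment assignment. That concerns interim data, not knowledge of one participant's arm.
- Section 6.16 covers coded records and custody of the master list, not masking of the PI.

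None of these masks the PI at adjudication.

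**3. Which outcomes pass through the rule?** Alcohol dependence and SCID anxiety remission do. Relapse status, drinking days, drinks per drinking day and hazardous drinking come from the TLFB, and the latent anxiety factors come from questionnaires, so these do not.

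**4. How large could the effect be?** The inputs are:
- 100 per arm, the figure Section 7.8 uses for its own power statement, assumed here to be the number with a follow-up SCID;
- a true dependence rate of 30% in both arms (assumption);
- a share *f* of follow-up diagnoses reaching the PI (assumption; not in the documents);
- a net 25% of those tipped one way, taken as the difference between arms (assumption).

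Standard error of the arm difference: sqrt(2 × 0.3 × 0.7 / 100) = 0.0648, or 6.5 points.

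Spurious difference: 0.25 × *f*. In standard errors, d = 0.25 × *f* / 0.0648. Two-sided type I error is P(|Z + d| > 1.96).

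| Share adjudicated, *f* | Shift (points) | d | Type I error |
|---|---|---|---|
| 2% | 0.5 | 0.08 | 5.1% |
| 5% | 1.25 | 0.19 | 5.4% |
| 10% | 2.5 | 0.39 | 6.7% |
| 20% | 5.0 | 0.77 | about 12% |

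If 25% were tipped in opposite directions in the two arms, each shift would double. The row for 5% would then read as the row for 10% does now, and the row for 10% as the row for 20%.

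**5. Which rows are plausible?** Follow-up questions refer to the time since the last assessment, so dependence disputes should arise almost only among people who drank. At the 53% relapse that Section 7.5 assumes for CBT-AR, 10% to 20% of all cases means 10/53 = 19% to 20/53 = 38% of drinkers failing consensus. At the 21% assumed for CBT-DC it means 10/21 = 48% to 20/21 = 95%. The assumed 30% dependence rate also exceeds that 21% any-relapse rate. The lower rows are easier to reconcile with the plan's own figures.

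**The case against.** The strongest reply is that the reach is small. The TLFB outcomes that Section 7.5 makes primary are untouched, and the power calculation rests on relapse. The PI acts only after consensus fails, on an instrument that Section 6.4.1 describes as essentially a checklist. Supervision belongs to the treatment phase, while follow-up SCIDs come one to eight months later. All of this stands and limits the point. It does not remove it: elapsed time is not masking, and Section 6.4.1 itself provides for sub-clinical and indeterminate ratings, so borderline cases are foreseen.

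A reader might infer three stronger things that the documents do not support.
- *That the trial's main result is compromised.* Under Section 7.5 the primary outcomes do not pass through this rule.
- *That both SCID outcomes would be pushed toward CBT-DC.* CBT-DC is favoured for alcohol. The dose logic of Sections 2.4 and 7.8 would lead one to expect the greatest anxiety reduction in CBT-AR, so any bias in anxiety remission could run the other way.
- *That the double-scoring of SCIDs is unblinded too*, because the co-investigator overseeing it also oversees therapy fidelity. Double-scoring covers 15% of interviews and serves to index reliability; nothing says it changes a diagnosis. Fidelity review covers a random 15% of sessions, and Section 6.5.4 records that it passed to someone else in September 2016.

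**Conclusion.** The point holds as a gap in outcome masking with limited reach. A stated rule undercuts the plan's own blinded assessor for disputed follow-up diagnoses. That the PI knows the arm is an inference, though a strong one; that masking at adjudication is not specified is a matter of record. The exposed outcomes are SCID alcohol dependence and SCID anxiety remission.

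The size of any bias cannot be determined. The range in the table, from near nominal up to about 12%, depends on an adjudication rate, a tipping rate and a dependence rate that the documents do not give, and its upper end requires dispute rates among drinkers that look high. It should be read as an illustration, not an estimate. The change is worth making because it is cheap and removes the question.

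**What to change.** In Section 6.8.2:
- Limit PI adjudication to diagnoses made before randomisation.
- For follow-up SCIDs, let the blinded assessor's rating stand when consensus fails. Alternatively, have the case settled from the videotape by an existing team member who does not know the arm. The make-up of the team is not stated, so the first option is the safer one to write in.
- State who is blinded at follow-up diagnosis.

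Section 5.1 already refers to recruitment through February 2020, so new wording may come too late for some follow-ups. For those already adjudicated, report the number by arm and add a sensitivity analysis of alcohol dependence and anxiety remission using the blinded assessor's rating from before adjudication. If that rating was not kept, the videotapes allow a masked re-rating. Sections 5.1 and 7.5 should also be reconciled on whether alcohol dependence is primary or secondary.

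The cost is protocol wording, a count and one extra analysis, with no new data collection; if the blinded rating is left to stand, no new staff are needed. The downside is less senior input on ambiguous follow-up cases.
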